**6.2 Dose Modifications for Non-Hematological Toxicity**

- 6.2.1 If a patient experiences non-hematological dose-limiting toxicity as defined in [Section 5.4.1](#), the treatment will be held. If the toxicity resolves to meet eligibility parameters or baseline within 14 days of drug discontinuation, the patient may resume treatment at a reduced dose as outlined in the dosing nomogram table in [Appendix IV](#). Doses reduced for toxicity will not be re-escalated, even if there is minimal or no toxicity with the reduced dose.
- 6.2.2 If a non-hematologic dose-limiting toxicity as defined in [Section 5.4.1](#) does not resolve to meet eligibility or baseline parameters within 14 days of drug discontinuation, the patient must be removed from protocol therapy. Any Grade 1 visual disturbance that persists for  $\geq 4$  weeks and does not resolve to meet eligibility or baseline parameters within  $\geq 4$  weeks of drug discontinuation must be removed from protocol therapy.
- 6.2.3 If non- hematologic dose-limiting toxicity recurs in a patient who has resumed treatment at the reduced dose, the patient must be removed from protocol therapy.

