**5.4.1 Non-Hematological Dose-Limiting Toxicity**

- 5.4.1.1 Any Grade 3 or greater non-hematological toxicity attributable to the investigational drug with the specific exclusion of:
- Grade 3 nausea and vomiting of < 3 days duration
  - Grade 3 liver enzyme elevation, including ALT/AST/GGT that returns to

levels that meet initial eligibility criteria or baseline within 7 days. See [Section 6.3](#), and [Appendix XI](#) for values that represent thresholds between CTCAE grades.

Note: For the purposes of this study the ULN for ALT is defined as 45 U/L regardless of baseline.

- Grade 3 or 4 fever < 5 days duration.
- Grade 3 infection < 5 days duration.
- Grade 3 hypophosphatemia, hypokalemia, hypocalcemia or hypomagnesemia responsive to supplementation

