
>10.0 mg/dL (>3.2 mmol/L) and/or significant alteration in baseline renal function and/or Grade 3 hypercalcemia
	
Erdafitinib should be discontinued permanently. (In situations where the subject is having clinical benefit and the study chair agrees that re-starting drug is in the best interest of the subject, the drug may be re-introduced at the reduced dose level outlined in Appendix IV if appropriatec. Follow other recommendations described above.)
	
Medical management as clinically appropriate.

Note: These are general guidelines that are based on emerging data and consensus experience of participating investigators and/or the experts in the field. The treating physicians must use clinical judgment and local standard of care to decide the best way to manage phosphate elevation. If sevelamer hydrochloride is not available, the use of other phosphate binders (non-calcium containing) based on the local standard is recommended. These guidelines will be updated based on emerging data. Additional information on phosphorous in foods by class of food can also be found at www.permanente.net/homepage/kaiser/pdf/42025.pdf. Additional information for phosphate management and diet can be found the National Kidney Foundation website (http://www.kidney.org/atoz/content/phosphorus.cfm) a. Drug interruptions for hyperphosphatemia suggested to be 7 days duration
		

b. Persistent hyperphosphatemia is considered to be more than 1 sequential phosphate value of  $\geq 7$  mg/dL

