Grade 3	Immediately stop erdafitinib and promptly refer subject to an ophthalmologist for evaluation with an ophthalmologic exam	
 
• Hold erdafitinib until eye exam is completed. If vision change is determined to be unrelated to erdafitinib, contact the study chair to discuss restarting of erdafitinib. Otherwise <math>\geq</math> Grade 3 visual disturbance will be considered a DLT and require a dose reduction as per Section 6.2 if resolves within 4 weeks.
 
• Follow specific treatment as per the ophthalmologist's recommendation.
 
• Monitor for recurrence every 1-2 weeks for a month and as clinically appropriate thereafter.
 
• If recurs, consider permanent discontinuation.
 

Grade 4	Permanently discontinue erdafitinib and promptly refer subject to an ophthalmologist for evaluation with an ophthalmologic exam	
 
• Refer to Section 13.0 for reporting guidelines; monitor resolution of eye finding until complete resolution, stabilization, or other off-study criteria are met (see Section 10.1)
 

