## 10.0 **CRITERIA FOR REMOVAL FROM PROTOCOL THERAPY AND OFF STUDY CRITERIA**

### 10.1 **Criteria for Removal from Protocol Therapy**

- a) Clinical (including physical examination or serum tumor markers) or radiographic evidence of progressive disease (See [Section 12](#)).
- b) Adverse Events requiring removal from protocol therapy (See [Section 6](#)).
- c) Refusal of protocol therapy by patient/parent/guardian
- d) Non-compliance that in the opinion of the investigator does not allow for ongoing participation.
- e) Completion of 26 cycles of therapy.
- f) Physician determines it is not in the patient’s best interest.

- g) Repeated eligibility laboratory studies (CBC with differential, bilirubin, ALT (SGPT) or serum creatinine) are outside the parameters required for eligibility prior to the start of protocol therapy (See [Section 8.1](#)).
- h) Study is terminated by Sponsor.
- i) Pregnancy
- j) Patient did not receive protocol treatment after study enrollment

**Patients who are removed from protocol therapy during cycle 1 should continue to have the required observations in [Section 8.1](#) until the originally planned end of the cycle or until all adverse events have resolved per [Section 13.4.4](#), whichever happens LATER. The only exception is with documentation of the patient's withdrawal of consent from the APEC1621SC screening protocol. Patients who are removed from protocol therapy in subsequent cycles should have the necessary observations to ensure adequate clinical care.**

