**APPENDIX IV: ERDAFITINIB DOSING NOMOGRAM**

Erdafitinib Dose Assignment: 4.7 mg/m^2/dose once daily (Maximum dose of 8 mg per day)

BSA (m^2)	Erdafitinib Dose (mg/dose) once daily	Dose Reduction For Toxicity (mg/dose) once daily
0.53-0.74	3	Off Protocol Therapy
0.75-0.96	4	3
0.97-1.17	5	3
1.18-1.38	6	4
1.39-1.59	7	5
≥ 1.6	8	6

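### For a drug-related Grade 3 visual disturbance that resolves on days 15 to 28, Section 6.2.2 requires removal while the visual table requires a reduced dose, and precedence is not explicit

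*Combined protocol and SAP*

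**What the plan says.** **DLT definition (5.4.1.1).** A DLT is "Any Grade 3 or greater non-hematological toxicity attributable to the investigational drug with the specific exclusion of" five groups of events: brief nausea and vomiting, liver enzymes that recover, brief fever, brief infection, and low electrolytes that respond to supplementation. None concerns the eye.

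**General rule (6.2).** Under 6.2.1, treatment may resume at the reduced dose in Appendix IV if the DLT resolves within 14 days. Under 6.2.2, if it "does not resolve to meet eligibility or baseline parameters within 14 days of drug discontinuation, the patient must be removed from protocol therapy". The one visual carve-out in 6.2.2 begins "Any Grade 1 visual disturbance that persists for" 4 weeks or more, and is limited to that grade. Under 6.2.3, a DLT that recurs at the reduced dose means removal.

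**Visual-disturbance table (unnumbered, after the nail tables of 6.7).** In the Grade 3 row the drug is stopped at once. Unless the event is judged unrelated, the "visual disturbance will be considered a DLT and require a dose reduction as per" "Section 6.2 if resolves within 4 weeks". On recurrence, the row says only that a permanent stop should be considered. The Grade 2 row also uses 4 weeks and also cites 6.2.

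**Linked text.** Criterion 10.1(b) is "Adverse Events requiring removal from protocol therapy (See" Section 6), meaning Section 6 as a whole. In Appendix IV the reduced-dose entry for BSA 0.53–0.74 m² is "Off Protocol Therapy"; every other band lists a single reduced dose. Section 9.1.1 (Patient Care Implications) says eye findings are managed by a dose-modification table in Section 6.8, but no section carries that number.

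**Dry skin.** For Grade 3, Section 6.5 restarts at Grade 1 or less, or baseline. Section 6.6, on skin disorders generally, restarts at tolerable Grade 2 or less and cites 6.2.

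**The concern.** Two mandatory instructions cover the same event with different time limits, and the row with the longer limit cites the section that sets the shorter one. When a Grade 3 eye event is still unresolved after day 14, one passage says the child must come off therapy and the other keeps a reduced dose open for another two weeks.

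This matters most for safety. Section 2.3.1 reports no prior pediatric experience with the drug, and central serous retinopathy is the adverse event of special interest in 13.3.1. Criterion 10.1(b) takes its content from Section 6, so the ambiguity carries into removal from protocol therapy and into later drug exposure.

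**Working it through.** The plan gives no figure on this point. The check is a side-by-side reading, followed by an interval check.

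**Step 1. Is the event inside 6.2.2?** Yes. It is Grade 3, non-hematological and attributable. None of the 5 exclusion groups in 5.4.1.1 is ocular, and the Grade 3 row itself calls it a DLT.

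**Step 2. Does 6.2.2 exempt it?** No. The carve-out names Grade 1 only.

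**Step 3. Compare outcomes by day of resolution.** Day counts run from the drug stop, and 4 weeks = 28 days.

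| Resolved on | Section 6.2 | Grade 3 visual row | Agree? |
|---|---|---|---|
| Day 14 or earlier | Reduced dose allowed | Reduced dose | Yes |
| Days 15–28 | Removal | Reduced dose | No |
| After day 28 | Removal | No reduction provided for | No contradiction |

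Conflict window: 28 − 15 + 1 = 14 days.

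**Step 4. Who can be affected?** The two outcomes differ only if a reduced dose exists. At BSA 0.53–0.74 m² none is listed, so both routes end in removal. A patient already on the single reduced dose has no further listed reduction. That leaves patients with BSA of at least 0.75 m² who have not already been reduced.

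**Step 5. Grade 2 visual events.** Section 6.2.2 covers DLTs only. A Grade 2 event is in conflict only if it meets 5.4.1.3, that is, it lasts at least 7 days and is significant or intolerable enough to need interruption.

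**Step 6. Does any text set precedence?** Section 10.1(b) refers to Section 6 as a whole. The visual row refers back to 6.2. Section 9.1.1 points to a section number that does not exist. The general note deferring to judgment, "The treating physicians must use clinical judgment and local standard of care to decide the best way to manage phosphate elevation", concerns phosphate only.

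**Step 7. Effect on the statistics.** The primary rule is at least 3 responses in 20:

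P(X ≥ 3) = 1 − Σ C(20,k) pᵏ(1−p)²⁰⁻ᵏ, summed over k = 0 to 2.

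At p = 0.05 this is 0.0755 (the plan states alpha 10%). At p = 0.25 it is 0.9087 (the plan states power 90%). Under 11.5, an eligible patient needs one dose to be evaluable, so a removed patient and a dose-reduced patient both stay among the 20. Section 11.6 does the same for toxicity. Section 11.4 tabulates worst grade, and the event is a DLT under either rule. Under 11.7, removal from therapy is not a PFS event.

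**Step 8. Dry skin.** Take a child with no dry skin at baseline who improves from Grade 3 to tolerable Grade 2. Section 6.6 permits restart; 6.5 does not yet. The test in 6.2.1, which 6.6 cites for the reduction, is different again: eligibility parameters or baseline.

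**The case against.** The strongest reply is that a specific table overrides a general rule. Section 9.1.1 supports this: the visual table is the only one that fits its reference, and the row's citation of 6.2 could be meant only for how to reduce the dose. The wrong section number proves little by itself, since the contents list also omits 7.6, which exists. So it would be too strong to say that nothing bears on precedence. But 9.1.1 states no override, and 6.2.2 does deal with visual events and extends the time for Grade 1 only.

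Second, the 14-day window is not shown for every case. The table does not say when its 4 weeks start. Section 6.2.2 tests resolution against eligibility or baseline, while the row says only that the event resolves. An eye event outside the conditions named in 4.2.9 might arguably meet the 6.2.2 test before symptoms have gone. Both points stand as assumptions.

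Third, oversight is close. Suspected DLTs go to the Study Chair within 24 hours (5.3), dose modifications must be notified (6.0), and study leadership reviews the data weekly (14.4.2). A reader might infer that sites cannot apply 10.1(b) at all; these channels show that goes too far. They limit variation between sites but supply no rule.

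Fourth, a reader might see a second contradiction between 6.2.3 and the recurrence line of the Grade 3 row. The two can be read together, with 6.2.3 governing a DLT that recurs at the reduced dose and the row governing other recurrences. The row does not state its scope, so this is an ambiguity only.

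Fifth, on dry skin, reaching Grade 1 also satisfies the 6.6 threshold, so waiting for 6.5 breaches nothing. The two sections differ in strictness, which makes this point minor.

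**Conclusion.** The contradiction is in the text and should be fixed. For a drug-related Grade 3 visual disturbance, 6.2.2 and the visual table give opposite outcomes when resolution falls on days 15 to 28. This rests on three conditions:

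- the table's 4 weeks start when the drug is stopped, which is plausible because the row requires an immediate stop;
- resolution means the same thing in both places;
- the patient still has a reduced dose listed in Appendix IV.

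Confidence is high for the textual mismatch. The recurrence and dry-skin points are lesser.

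The number of patients affected cannot be derived, because the documents give no time to resolution for Grade 3 visual events. The trial is capped at 49 patients, and those affected would be a subset with a drug-related Grade 3 eye event, late resolution and an available reduction.

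A reader might infer harm to the primary decision or to the tolerability results. The documents do not support that: the A'Hern rule, evaluability for response and toxicity, and the planned toxicity tables are the same under either rule. The effect is on patient safety, removal under 10.1(b) and later exposure.

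**What to change.** Amend Section 6 so that each visual event and grade has one hold limit, one definition of resolution and one recurrence rule:

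- Reconcile 6.2.2 with the Grade 2 and Grade 3 visual rows.
- State when the 4 weeks begin and what counts as resolved.
- State whether event-specific tables override 6.2.
- Number the visual table, and correct the Section 6.8 reference in 9.1.1.
- Say which recurrences the Grade 3 row covers, given 6.2.3.
- Align the restart thresholds in 6.5 and 6.6 with each other and with 6.2.1.

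The clinical team decides which rule stands; this point proposes none. The cost is a text change at the next amendment, with no added visits, procedures or patients.

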**6.3 Dose Modifications for Hepatic Adverse Events**

- 6.3.1 If a patient experiences Grade 3 ALT/AST/GGT, treatment will be held. If toxicity resolves to meet eligibility criteria within 7 days, the drug may be resumed at the same dose. Grade 3 ALT/AST/GGT that persists  $\geq 7$  days will be considered dose-limiting and require dose modification per [Section 6.2](#). See [Appendix XI](#) for values that represent thresholds between CTCAE grades.
- 6.3.2 If a patient experiences Grade 4 ALT/AST/GGT, the patient must be removed from protocol therapy. See [Appendix XI](#) for values that represent thresholds between CTCAE grades.

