4.1.7 Organ Function Requirements

4.1.7.1 Adequate Bone Marrow Function Defined as:

- a. For patients with solid tumors without known bone marrow involvement:
  - Peripheral absolute neutrophil count (ANC)  $\geq 1000/\text{mm}^3$
  - Platelet count  $\geq 100,000/\text{mm}^3$  (transfusion independent, defined as not receiving platelet transfusions for at least 7 days prior to enrollment)
  - Hemoglobin  $\geq 8.0$  g/dL at baseline (may receive RBC transfusions)
- b. Patients with known bone marrow metastatic disease will be eligible for study provided they meet the blood counts in 4.1.7.1.a (may receive platelet or pRBC transfusions provided they are not known to be refractory to red cell or platelet transfusions). These patients will not be evaluable for hematologic toxicity.

4.1.7.2 Adequate Renal Function Defined as:

- Creatinine clearance or radioisotope GFR  $\geq 70\text{ml}/\text{min}/1.73 \text{ m}^2$  or
- A serum creatinine based on age/gender as follows:

Age	Maximum Serum Creatinine (mg/dL)	
	Male	Female
1 to < 2 years	0.6	0.6
2 to < 6 years	0.8	0.8
6 to < 10 years	1	1
10 to < 13 years	1.2	1.2
13 to < 16 years	1.5	1.4
$\geq 16$ years	1.7	1.4

The threshold creatinine values in this Table were derived from the Schwartz formula for estimating GFR (Schwartz et al. J. Peds, 106:522, 1985) utilizing child length and stature data published by the CDC.

4.1.7.3 Adequate Liver Function Defined as:

- Bilirubin (sum of conjugated + unconjugated)  $\leq 1.5$  x upper limit

- of normal (ULN) for age
- SGPT (ALT)  $\leq$  135 U/L. (For the purpose of this study, the ULN for SGPT is 45 U/L.)
- Serum albumin  $\geq$  2 g/dL

4.1.7.4 Adequate Cardiac Function Defined as:

- QTc interval  $\leq$  480 milliseconds

4.1.7.5 Adequate Pulmonary Function Defined as:

- Pulse oximetry  $>$  94% on room air if there is clinical indication for determination (e.g. dyspnea at rest).

4.1.8 Patients must be able to swallow intact tablets.

4.1.9 Informed Consent: All patients and/or their parents or legally authorized representatives must sign a written informed consent. Assent, when appropriate, will be obtained according to institutional guidelines.

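### Sections 5.4.1.1 and 6.3.1 test Grade 3 ALT/AST/GGT differently, 6.3.1 overlaps itself at day 7, and its restart test is undefined for AST and GGT

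*Combined protocol and SAP*

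**What the plan says.** Section 5.4.1.1 starts from a broad default. A DLT is "Any Grade 3 or greater non-hematological toxicity attributable to the investigational drug with the specific exclusion of" a short list of exceptions, and Section 5.4 requires at least possible attribution to protocol therapy. The hepatic exception covers "Grade 3 liver enzyme elevation, including ALT/AST/GGT that returns to" "levels that meet initial eligibility criteria or baseline within 7 days", and it points the reader to Section 6.3 and Appendix XI.

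Section 6.3.1 holds treatment for Grade 3 ALT/AST/GGT and then gives two sentences. The first is on restart: "If toxicity resolves to meet eligibility criteria within 7 days, the drug may be resumed at the same dose". The second says that Grade 3 lasting 7 days or longer "will be considered dose-limiting and require dose modification per" Section 6.2.

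Section 6.2.1 covers every non-hematological DLT defined in 5.4.1: "If the toxicity resolves to meet eligibility parameters or baseline within 14 days of drug discontinuation, the patient may resume treatment at a reduced dose". Section 6.2.2 removes the patient if that recovery is not reached in 14 days.

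Section 4.1.7.3 caps ALT at 135 U/L and gives the reference: "For the purpose of this study, the ULN for SGPT is 45 U/L". It also limits bilirubin and albumin, but neither AST nor GGT. Appendix XI has grade cut-offs for all three enzymes. The schedule in Section 8.1 lists ALT and bilirubin, and neither AST nor GGT.

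**The concern.** One test asks how far the value has fallen; the other asks how long the grade lasted. They agree only when an enzyme leaving Grade 3 drops straight into the eligible range. Because 5.4.1.1 refers to 6.3, the two sections are meant to work as one rule.

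The classification has consequences. A DLT leads to the reduced dose in Appendix IV, or to the end of protocol therapy in the 0.53-0.74 m² band. Reduced doses are not re-escalated (6.2.1), and a recurrent DLT at the reduced dose means removal (6.2.3). A DLT must be reported to the Study Chair within 24 hours (5.3) and is entered in the study database (14.4.2). Tolerability is a secondary aim (1.2.2), there is no prior experience in children (2.3.1), and Section 11.2 relies on close monitoring to confirm that the chosen dose is tolerable.

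**Working it through.** No sample-size, power or event figure is involved, so there is none to reproduce. The check is of thresholds and logic.

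**Inputs.** ALT eligibility limit 135 U/L, with ULN 45 (4.1.7.3). ALT Grade 2 is 136-225 and Grade 3 is 226-900 U/L; AST Grade 2 is 151-250 U/L with ULN 50 (Appendix XI). The recovery and duration tests come from 5.4.1.1, 6.2.1 and 6.3.1, and the laboratory schedule from 8.1 and Appendix V.

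**Step 1: cut-offs.** ALT: 135/45 = 3, 225/45 = 5, 900/45 = 20. AST: 150/50 = 3, 250/50 = 5, 1000/50 = 20. The grading agrees with the stated ULNs. The ALT Grade 2 band lies wholly above 135 U/L. An eligible patient cannot have a baseline above 135, so the baseline alternative in 5.4.1.1 can never make Grade 2 ALT count as recovered.

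**Step 2: attributable Grade 3 ALT, each section read literally.** Let *a* be the day ALT leaves Grade 3 and *b* the day it reaches 135 U/L or less, with *b* ≥ *a*. Then:
- 5.4.1.1: DLT if *b* > 7.
- 6.3.1, second sentence: dose-limiting if *a* ≥ 7.
- 6.3.1, first sentence: same dose allowed if *b* ≤ 7.

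| Course | DLT under 5.4.1.1 | Meets 6.3.1 dose-limiting sentence | 6.3.1 allows same dose |
|---|---|---|---|
| *a* < 7, *b* ≤ 7 | No | No | Yes |
| *a* < 7, *b* > 7 | Yes | No | No |
| *a* ≥ 7, *b* > 7 | Yes | Yes | No |
| *a* = 7, *b* = 7 | No | Yes | Yes |

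Running *a* from 1 to 14 and *b* from 1 to 20 gives these four patterns and no others (27 + 78 + 83 + 1 = 189 combinations; the counts describe the grid, not how often patients follow each course). Rows 1 and 3 are consistent.

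Row 2 is the gap. Take ALT of 300 U/L that falls to 180 U/L before day 7 and is still 180 on day 8. It fails the 5.4.1.1 exemption, so 6.2 applies. In 6.3.1 it meets neither sentence, and that section names no other dose and no removal rule.

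**Step 3: day 7.** In row 4 the two sentences of 6.3.1 both apply. This assumes that the duration of Grade 3 is counted to the first value below Grade 3. The boundary can be reached in practice: cycle 1 chemistry is weekly, with draws on days 8, 15 and 22 in Appendix V, and 15 − 8 = 7. Section 6.3.1 sets no recheck interval, whereas 6.1.1 does for blood counts.

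**Step 4: isolated AST or GGT.**
- 5.4.1.1 and 6.2.1: the eligibility route has no value to apply, so only the baseline route is left.
- 6.3.1: eligibility is the only route. With no limit set, a site could read the test as automatically met or as impossible to meet.
- 8.1: neither enzyme is scheduled, so a baseline may not exist. Where one does, eligibility does not prevent it from being Grade 2.

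For AST and GGT, then, DLT status can be indeterminate; the certain DLT in row 2 is an ALT result.

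**The case against.** The strongest reply is that 5.4.1.1 is the definition of a DLT and 6.3.1 is not. Section 6.3.1 names one dose-limiting case without saying it is the only one, and it never declares any other Grade 3 event to be a non-DLT. Read together, the sections give the 300-to-180 course one outcome: DLT, hold, then reduced dose or removal under 6.2. This stands. A reader might infer that such a patient has no rule anywhere, or that 6.3.1 expressly contradicts the DLT definition; the text supports neither. What the reply does not remove is that no statement gives 5.4.1.1 precedence, and that 6.3.1, the specific hepatic section, is silent for this course. It also leaves day 7 and AST/GGT unresolved.

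A second reply is that little depends on it. Section 11 has no DLT-based decision rule, and Section 11.4 tabulates toxicity by type and worst grade. DLTs and dose modifications go to the Study Chair (5.3, 6.0), and leadership reviews the evaluations weekly (14.4.2). This stands too and limits the harm, although central review still needs one rule to apply.

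A reader might also try to size the problem. Three figures invite it, and none serves:
- The agent's risk list places ALT and AST increases in its category of up to 20%, which is not restricted to Grade 3.
- The 27.3% in Study HCC1001 is 3 of 11 adults with advanced liver cancer, without regard to grade. No Grade 3 or 4 event there was judged drug-related.
- The Appendix IV reductions run from 25% (8 to 6 mg) to 40% (5 to 3 mg). To be the size of this conflict, one section would have to give the same dose and the other a reduced dose to the same patient. In row 2, 6.3.1 withholds the same dose; the direct clash is confined to day 7.

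**Conclusion.** The point holds as an inconsistency with a gap, and it is worth correcting. Three things are established from the text:
- 5.4.1.1 and 6.3.1 use different tests, which separate for ALT that leaves Grade 3 before day 7 but is still above 135 U/L after it.
- The two sentences of 6.3.1 overlap at exactly day 7.
- The 6.3.1 restart test for isolated AST or GGT refers to a criterion that the protocol does not contain.

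The ALT result assumes attribution to protocol therapy and a baseline within the eligibility limit. The effect is on DLT classification, consistency of restart and removal decisions, and tolerability reporting. The rule of at least 3 responses in 20 patients is untouched. The documents give no rate of attributable Grade 3 enzyme events at this dose in children, so the number affected is unknown and may be small. Isolated AST or GGT events would come only from unscheduled tests.

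**What to change.** Reconcile Sections 4.1.7.3, 5.4.1.1, 6.2, 6.3.1 and 8.1 with Appendix XI. The DLT definition and the hepatic section should share one recovery test and one 7-day boundary that does not overlap, so that every Grade 3 enzyme course has one DLT status and one stated route. The AST and GGT test should refer to something the protocol defines. Which existing wording governs is for the study committee; this review does not propose a level or a clinical rule.

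The cost is a short wording change in an amendment, with no change to sample size or analysis. If the committee keeps baseline as the AST/GGT reference, Section 8.1 would have to call for those baseline values, which adds a test. If Grade 3 enzyme events have already been classified, the study report should state which test was used.
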